6.1.4.2 Prior Antibiotic Therapy

Subjects will be excluded from the CE populations if they meet the prior antibiotic exclusion criteria:

Exclusion Criterion 1: Has received 1 or more dose(s) of a potentially effective systemic antibacterial treatment within the 72 hours prior to the first dose of test article (a subject will be considered to have received a potentially effective systemic antibacterial treatment if the pathogen identified as causing infection is shown to be susceptible to the antibacterial given or, in the circumstance where a pathogen is not identified, if the antibacterial agent is approved for treatment of pneumonia or is known to have activity against any of the leading

causes of CABP [eg, *Streptococcus pneumoniae*, *Haemophilus influenzae*, *Moraxella catarrhalis*, *Staphylococcus aureus*, *Legionella pneumophila*]. EXCEPTION: Subjects may be eligible despite prior antibacterial therapy if they have been treated with a single dose of a short-acting antibacterial (ie, an antibacterial whose standard dosing regimen is more frequent than once per day, see [Appendix 1](#) of the protocol). Enrollment of subjects who received a single dose of an allowed short-acting antibiotic within the 72 hours prior to the first dose of test article will be limited to no more than 25% of randomized subjects.

6.1.4.3 Concomitant Antibiotic Therapy

Subjects who receive any systemic concomitant antibiotic therapy from the time of the first dose of test article through the time of the last dose of test article at EOT and through the PTE Visit with a spectrum of activity against the known or potential infecting pathogen(s) responsible for the CABP under study will be excluded from the CE-EOT and CE-PTE populations, respectively, unless the subject receives the antibiotic therapy for treatment of the CABP due to insufficient therapeutic effect of the test article (ie, for progression or development of new symptoms of CABP or development of infectious complications of CABP).

Subjects who receive a systemic concomitant antibiotic that is not effective against the baseline pathogen, or if no pathogen is isolated, and the antibiotic does not have activity against CABP pathogens, will be included in the CE-EOT and CE-PTE populations.

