5.2.2 Secondary Efficacy Outcomes

5.2.2.1 Investigators Assessment of Clinical Response

The investigator will make an assessment of Clinical Response at the EOT and PTE Visits, based on the definitions below. The secondary efficacy outcome is the overall assessment of clinical response at PTE (derived from the investigator assessments at the EOT and PTE Visits) in the ITT and CE-PTE populations as defined in [Table 3](#).

EOT Visit

At the EOT Visit (on the calendar day of, or within 2 days following the last dose of test article), the investigator will indicate the clinical status of the infection under study as detailed below.

Clinical Success: the subject is alive and the infection is sufficiently resolved such that further antibacterial therapy is not needed. These subjects may have some residual findings related to infection (ie, cough) requiring ancillary (ie, non-antibiotic) treatment (eg, expectorant). In order for the subject to be considered a Clinical Success at EOT, the subject may not meet any criteria for Clinical Failure or Indeterminate at EOT.

Clinical Failure: the subject requires alternative antibacterial treatment for CABP prior to EOT related to either (a) progression or development of new symptoms to CABP or (b) development of infectious complications of CABP (eg, empyema, lung abscess) or (c) subject developed an AE that required discontinuation of study therapy prior to the EOT. Other reasons for clinical failure are:

- Subject is receiving antibacterial therapy that may be effective for the infection under study for a different infection from the one under study.
- Death prior to EOT.

Indeterminate: the clinical response to test article could not be adequately inferred due to:

- Subjects were not seen for EOT evaluation because they withdrew consent, were lost to follow-up, other reason (specify).
- Other specified reason.

PTE Visit

At the PTE Visit (5 to 10 days after the subject's last day of study therapy) the investigator will indicate one of the following outcomes relating to the primary infection under study:

Clinical Success: survival after completion of a test article regimen without receiving any systemic antibacterial therapy other than test article, resolution of signs and symptoms of the infection present at Screening with no new symptoms or complications attributable to CABP and no need for further antibacterial therapy.

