Clinical Failure: the subject requires alternative antibacterial treatment for CABP prior to PTE related to either (a) progression or development of new symptoms of CABP or (b) development of infectious complications of CABP (eg, empyema, lung abscess). Other reasons for clinical failure are:

- The subject is receiving antibiotics that may be effective for the infection under study for a different infection from the one under study.
- Death prior to PTE.

Indeterminate: the clinical response to test article could not be adequately inferred due to:

- Subjects were not seen for PTE evaluation because they withdrew consent, were lost to follow-up, other (specify).
- Other specified reason.

Overall Clinical Response at PTE (based on the investigator's assessment) is determined as follows from the investigator's assessments at the EOT and PTE Visits:

Table 3. Investigator's Assessment of Clinical Response

EOT Visit	PTE Visit	Overall Assessment of Clinical Response at PTE Visit
Success	Success	Success
Success	Failure	Failure
Success	Indeterminate	Indeterminate
Failure	Success	Failure
Failure	Failure	Failure
Failure	Indeterminate	Failure
Indeterminate	Success	Indeterminate
Indeterminate	Failure	Failure
Indeterminate	Indeterminate	Indeterminate

Abbreviations: EOT = end of treatment; PTE = post-therapy evaluation.

For the ITT population, the proportion of ITT subjects with a Clinical Success is defined using the following formula (where the denominator adds to the total number of subjects in the ITT population):

Number of subjects with Clinical Success

(Number of subjects with Clinical Success + Number of subjects with a Clinical Failure + Number of subjects with an Indeterminate response)

By definition, subjects in the CE-EOT and CE-PTE populations cannot have an Indeterminate response. Thus, for the CE-EOT and CE-PTE populations, the proportion of subjects with a Clinical Success is defined using the following formula:

Number of subjects with Clinical Success

(Number of subjects with Clinical Success + Number of subjects with a Clinical Failure)

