6.1.4.1 Diagnosis of CABP

To be included in the CE-EOT and CE-PTE populations, subjects must meet the following protocol defined inclusion criteria that describe the CABP:

Inclusion Criterion 3: Has at least 3 of the following symptoms:

- Cough
- Production of purulent sputum
- Dyspnea (shortness of breath)
- Pleuritic chest pain.

Inclusion Criterion 4: Has at least 2 of the following abnormal vital signs:

- Fever or hypothermia documented by the investigator (po or rectal temperature $> 38.0^{\circ}\text{C}$ [100.4°F] or $< 36.0^{\circ}\text{C}$ [95.5°F])

- Hypotension with systolic blood pressure (SBP) < 90 mmHg
- Heart rate > 90 bpm
- Respiratory rate (RR) > 20 breaths/minute.

Inclusion Criterion 5: Has at least 1 clinical sign or laboratory finding associated with CABP:

- Hypoxemia Partial pressure of arterial oxygen (PaO₂) < 60 mmHg by arterial blood gas (ABG)
- Physical examination findings of pulmonary consolidation (dullness on percussion, bronchial breath sounds, egophony, rales, rhonchi, or decreased breath sounds)
- An elevated total white blood cell (WBC) count (> 12,000 cells/mm³) **or** leucopenia (WBC < 4,000 cells/mm³) **or** elevated immature neutrophils (> 15% band forms regardless of total peripheral WBC count).

Inclusion Criterion 6: Radiographically-confirmed pneumonia, ie, new or progressive pulmonary infiltrate(s) on chest X-ray (CXR) or chest computed tomography (CT) scan consistent with acute bacterial pneumonia within 24 hours prior to the first dose of test article.

If the imaging study is done more than 24 hours prior to the first dose of test article but within 48 hours, the subject will be included in the CE populations as long as the imaging study shows a new or progressive pulmonary infiltrate(s) consistent with acute bacterial pneumonia.

Inclusion Criterion 7: Have disease categorized as being PORT Risk Class II, III, or IV at Screening:

The Sponsor Medical Monitor will also review those subjects with a concomitant illness identified after baseline that could have presented at baseline as pneumonia. If it is determined that the subject does not have pneumonia but had another condition such as lung cancer at baseline, the subject will not be evaluable for the CE populations.

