6.1.4.4 Test Article Therapy

Subjects must meet all of the following to be included in the CE populations:

- Received at least 1 dose of active test article and the correct test article based on the randomization assignment.
- Study personnel involved in the assessment of efficacy remained blinded to study treatment, unless a treatment limiting adverse event occurred which required emergency unblinding.
- Evaluable failure: The subject received the first 3 doses of active test article (omadacycline group) or first 2 doses of active test article (moxifloxacin group) and the investigator classifies the subject as a Clinical Failure at the EOT Visit (CE-EOT population) or the overall Clinical Response (based on the investigator's assessment) at the PTE Visit (CE-PTE population) is Clinical Failure.
- Evaluable success: The subject received the first 4 doses of active test article (omadacycline group) or the first 3 doses of active test article (moxifloxacin group) and the investigator classifies the subject as a Clinical Success at the EOT Visit (CE-EOT population) or the overall Clinical Response (based on the investigator's assessment) at the PTE Visit (CE-PTE population) is Clinical Success.

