6.1.5 Microbiologically Evaluable (ME) Populations

The ME-EOT and ME-PTE populations will consist of all subjects in both the microITT and the CE-EOT and CE-PTE populations, respectively.

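### Should the clinically evaluable analysis at PTE restore failures who stopped treatment for an adverse event and were switched to another antibiotic?

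*Combined protocol and SAP*

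**What the plan says.** SAP 6.1.4.3 excludes from CE-PTE any patient who takes a systemic antibiotic active against the known or potential pathogen between first dose and the PTE Visit, "unless the subject receives the antibiotic therapy for treatment of the CABP due to insufficient therapeutic effect of the test article". A parenthesis closes that exception: "ie, for progression or development of new symptoms of CABP or development of infectious complications of CABP". For CE-EOT the window ends at the last dose of test article. Protocol 13.1 treats further therapy for the infection as concomitant medication.

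SAP 5.2.2.1 opens the EOT failure definition with "the subject requires alternative antibacterial treatment for CABP prior to EOT related to either" and lists three limbs. Limbs (a) and (b) are progression or new symptoms, and infectious complications. The third is "c) subject developed an AE that required discontinuation of study therapy prior to the EOT". Table 3 turns every EOT Failure into an overall Failure, whatever is recorded at PTE. The PTE definition has no AE limb: "the subject requires alternative antibacterial treatment for CABP prior to PTE related to either (a) progression or development of new symptoms of CABP", or infectious complications, plus death and antibiotics for another infection.

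Other CE rules bear on the same patients. For an evaluable failure, 6.1.4.4 asks for a minimum exposure: "The subject received the first 3 doses of active test article (omadacycline group) or first 2 doses of active test article (moxifloxacin group"). Section 6.1.4.5 waives the PTE visit window for EOT failures. Section 6.1.5 passes any CE exclusion on: "The ME-EOT and ME-PTE populations will consist of all subjects in both the microITT and the CE-EOT and CE-PTE populations, respectively".

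On analysis, SAP 10.1 tests Early Clinical Response in ITT, 10.2 lists sensitivity analyses for that outcome only, and 10.3 makes the PTE intervals descriptive, with no non-inferiority conclusion.

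**The concern.** The exception in 6.1.4.3 matches limbs (a) and (b) of the EOT failure definition and leaves out limb (c). Limb (c) sits under an opening clause about needing another antibacterial, so a limb (c) failure will normally have received one. The SAP therefore calls this patient a Failure in one section and removes the patient from CE-PTE in another.

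Within this group every patient removed is a failure. The removal depends on a post-randomisation event that may be related to treatment. If one drug forces more patients off therapy than the other, CE-PTE and ME-PTE understate that drug's failure rate. Evaluable sets are usually read beside ITT for agreement in a non-inferiority trial, so an understated difference there could give false comfort. Nothing in 10.2 or 10.3 shows the CE-PTE result with these patients put back.

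**Working it through.** **1. Where each kind of EOT failure ends up** (other CE criteria assumed met)

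| Reason for EOT Failure | Active replacement antibiotic | ITT at PTE | CE-EOT | CE-PTE |
|---|---|---|---|---|
| (a) or (b) | yes | Failure | Failure | Failure (exception applies) |
| (c) AE | yes, after last dose | Failure | Failure | excluded |
| (c) AE | yes, by the last dose | Failure | excluded | excluded |
| (c) AE | none | Failure | Failure | Failure (Table 3) |

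The rule affects only limb (c) failures who met the dose minimum and took an active replacement. CE-PTE keeps the last row, so its view of AE-driven failure is reduced and not abolished. The rules do not contradict each other: 6.1.4.4 and 6.1.4.5 set further conditions for inclusion and do not override 6.1.4.3.

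**2. The plan's own CE figures** (SAP 5.1.1)

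Farrington-Manning, 1:1, rate 79%, margin 10 points, one-sided alpha 0.0125, power 80%:

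n per arm = [z(1-alpha) x sqrt(sum of constrained p(1-p)) + z(power) x sqrt(sum of p(1-p))]^2 / margin^2

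This gives 638 in total, as stated. Then 638 x 0.80 = 510, or 255 per arm. At 85% in both arms the power is 80.7%, against 81% stated.

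**3. Size of the shift in CE-PTE**

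The documents give no limb (c) rate for this trial, so the counts below are assumptions. CE-PTE in this SAP includes PORT II ("Have disease categorized as being PORT Risk Class II, III, or IV at Screening"), so take 750 x 80% / 2 = 300 per arm, with 85% success (255/300). Restored failures add to the denominator only. If q is their share of the enlarged arm, the restored rate is 0.85(1 - q), so

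shift = -0.85 x (q omadacycline - q moxifloxacin).

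For 12 v 6: q = 12/312 = 3.85% and 6/306 = 1.96%, so the shift is -0.85 x 1.89 = -1.60 points. Unstratified Miettinen-Nurminen 95% intervals, as in SAP 10.1:

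| Restored, omadacycline v moxifloxacin | Rates | Difference, points (95% CI) |
|---|---|---|
| none | 255/300 v 255/300 | 0 (-5.77 to +5.77) |
| 6 v 6 | 255/306 v 255/306 | 0 (-5.95 to +5.95) |
| 15 v 15 | 255/315 v 255/315 | 0 (-6.16 to +6.16) |
| 12 v 6 | 255/312 v 255/306 | -1.60 (-7.62 to +4.43) |
| 6 v 12 | 255/306 v 255/312 | +1.60 (-4.43 to +7.62) |
| 3 v 6 | 255/303 v 255/306 | +0.83 (-5.08 to +6.73) |

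The last row uses the Phase 2 AE-discontinuation rates in protocol 9.1, 0.9% and 1.9% of 300. They come from another indication and comparator, and cover all AE discontinuations. If 300 is instead the count before exclusion, 12 v 6 moves the difference from +0.04 (245/288 v 250/294) to -1.67 (245/300 v 250/300; -7.79 to +4.45).

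**4. What ITT shows**

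With 375 per arm, six more AE failures on omadacycline, all other counts equal, lower its success rate by 6/375 = 1.6 points. ITT at PTE carries about the amount that CE-PTE omits.

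**5. If CE were used to test a margin**

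Suppose the true restored difference were exactly -10 points (75% v 85%), with 255 per arm and one-sided alpha 0.0125. The CE rates are then 0.75/(1 - q) and 0.85/(1 - q). The chance that CE passes is 1.1% at q = 2% v 2%, 1.9% at 3% v 2%, 3.4% at 4% v 2%, 14.6% at 7% v 2%, and 0.6% at 0.9% v 1.9%. Inflation needs a higher AE-forced rate on omadacycline. Protocol 22.4.3 also requires ITT to pass, and ITT counts these patients as Failures.

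**The case for a change.** The best case for acting is that no planned output isolates this rule. ITT at PTE also counts Indeterminates in the denominator and uses visits outside the window (SAP 8.6), so a gap between ITT and CE-PTE cannot be attributed to 6.1.4.3. CE-EOT is a different time point. The SAP 13.2 table of antibiotics taken up to PTE, with reasons, is confined to CE-PTE and so omits the excluded patients. SAP 10.3 already repeats one secondary outcome under other handling, namely mortality in patients of known status. One sentence, one flag and one table fixed before unblinding would cost little, and adding them later would look data-driven.

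The reading of 6.1.4.3 stands, and so does the point about attribution. The need for a change does not. The new table would be a descriptive interval beside another descriptive interval, on a set lying between two that are already reported. It would mix tolerability with drug effect, which is a fair reason for an evaluable set to leave these patients out. The counts are also recoverable: SAP 9.1 tabulates reasons for exclusion and lists them by patient, 10.3 summarises reasons for failure by arm, and 11.1 tabulates AEs leading to discontinuation. A reader who wants the restored rate can add those failures to the denominator, as in step 3.

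**Conclusion.** No change is called for. This is a fair trade-off: CE-PTE asks how the drug performs in patients whose outcome is not shaped by another active antibiotic, and ITT at PTE keeps everyone. Following the plan as written leaves its conclusions sound, because the primary analysis is unaffected and no margin is tested in CE-PTE.

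Each one-point imbalance in such failures moves the CE-PTE difference by about 0.85 points, in either direction. In the scenarios shown, the largest shift is about 1.7 points and the lowest limit is -7.79. This rests on 300 per arm, 85% success and assumed failure counts; only the Phase 2 pair has a source in the documents.

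One limit applies. The absence of a restoring analysis can be confirmed only for this FDA SAP. Protocol 22.4.4 promises sensitivity analyses of response at PTE and leaves those for the EMA to a separate SAP, where CE at PTE is co-primary. That plan was not available, so nothing is concluded about it.

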6.1.4.4 Test Article Therapy

Subjects must meet all of the following to be included in the CE populations:

- Received at least 1 dose of active test article and the correct test article based on the randomization assignment.
- Study personnel involved in the assessment of efficacy remained blinded to study treatment, unless a treatment limiting adverse event occurred which required emergency unblinding.
- Evaluable failure: The subject received the first 3 doses of active test article (omadacycline group) or first 2 doses of active test article (moxifloxacin group) and the investigator classifies the subject as a Clinical Failure at the EOT Visit (CE-EOT population) or the overall Clinical Response (based on the investigator's assessment) at the PTE Visit (CE-PTE population) is Clinical Failure.
- Evaluable success: The subject received the first 4 doses of active test article (omadacycline group) or the first 3 doses of active test article (moxifloxacin group) and the investigator classifies the subject as a Clinical Success at the EOT Visit (CE-EOT population) or the overall Clinical Response (based on the investigator's assessment) at the PTE Visit (CE-PTE population) is Clinical Success.

6.1.4.5 Clinical Outcome Assessment

Subjects must meet the following to be included in the CE populations:

- For the CE-EOT population:
 - Completed the investigator's assessment of clinical response (ie, was not deemed an indeterminate outcome) at the EOT Visit, and
 - The EOT Visit occurred on the day of, or within 2 days following the last dose of test article.
- For the CE-PTE population:
 - The overall Clinical Response (based on the investigator's assessment) at the PTE Visit is not Indeterminate.
 - The PTE Visit occurred 5 to 10 days after the last dose of test article, unless the subject was considered to be a Clinical Failure based on the investigator's assessment at the EOT Visit or the patient died after EOT and before PTE.

6.1.4.6 Baseline Medical Events

Subjects will be excluded from the CE populations if the investigator has documented in the eCRF that they meet any one of the following protocol-defined exclusion criteria at baseline (ie, prior to randomization):

Exclusion Criterion 2: Is known or suspected to have CABP caused by a pathogen that may be resistant to either test article (eg, *Klebsiella pneumoniae*, *Pseudomonas aeruginosa*, *Pneumocystis jiroveci*, obligate anaerobes, mycobacteria, fungal pathogens).

Exclusion Criterion 3: Suspected or confirmed empyema (a parapneumonic pleural effusion is not an exclusion criteria) or lung abscess.

Exclusion Criterion 4: Subjects with known or suspected hospital-acquired pneumonia (HAP) or healthcare-associated pneumonia (HCAP). HAP is defined as pneumonia with onset of clinical signs and symptoms \geq 48 hours after hospitalization in an acute in-subject health care facility. HCAP is defined as pneumonia acquired in a long-term care or subacute/intermediate healthcare facility (eg, nursing home) or in a subject admitted with pneumonia following a recent hospitalization (discharged within 90 days of current admission and previously hospitalized for \geq 48 hours).

Exclusion 11: Requires acute pharmacologic intervention to stabilize blood pressure (BP) and/or adequate tissue perfusion, OR has evidence of septic shock defined by ALL of the following:

- Fever or hypothermia documented by the investigator (po or rectal temperature $> 38.0^{\circ}\text{C}$ [100.4°F] or $< 36.0^{\circ}\text{C}$ [95.5°F])
- Heart rate > 90 beats/minute

- RR > 20 breaths/minute
- WBC > 12,000 cells/mm³ or < 4,000 cells/mm³ or > 10% immature (band) forms regardless of the total peripheral WBC count
- Hypotension with SBP < 90 mmHg despite an iv fluid challenge of 20-30 cc/kg over a 30-minute period
- Perfusion abnormalities that may include, but are not limited to, lactic acidosis (blood lactate concentration \geq 4 mmol/L), oliguria, or acute alteration in mental status.

Exclusion Criterion 12: Known or suspected primary or metastatic neoplastic lung disease, aspiration pneumonia, cystic fibrosis, bronchiectasis, bronchial obstruction (eg, post-obstructive pneumonia), chronic neurological disorder preventing clearance of pulmonary secretions, or severe chronic obstructive pulmonary disease (COPD).

6.1.5 Microbiologically Evaluable (ME) Populations

The ME-EOT and ME-PTE populations will consist of all subjects in both the microITT and the CE-EOT and CE-PTE populations, respectively.

6.2 Evaluability Review Team

6.2.1 Membership and Responsibilities

The Evaluability Review Team (ERT) will review both clinical and microbiological data for determination of criteria used to assess inclusion in the analysis populations and for determination of baseline and post-baseline pathogens. ERT members will be blinded to treatment assignment and will review the data concurrent with the conduct of the study. The ERT will be conducted in accordance with the ERT Process Document.

